5.8 Follow-up assessments

Ongoing AEs thought to be related to carfilzomib will be followed until the event has resolved to baseline, the event is assessed by the investigators to be stable, the patient is lost to follow up, the patient withdraws consent, or when it is determined the AE is not related to study drug.

5.9 Patient discontinuation

Patients will be removed from study continuation if the toxicities of therapy are deemed by the investigators to outweigh the potential benefit of therapy. Such toxicities may include severe thrombocytopenia (platelets < $10,000 \times 10^6$), acute kidney injury requiring renal replacement therapy, or severe hepatitis (ALT > 1000), or others deemed relevant to the individual patient by the investigators.

If patients discontinue study drug early, these patients may be replaced in the study by patients who are likely to complete at least 1 cycle of carfilzomib.

The investigators have the right to discontinue a patient from the study for any medical condition that the investigator determines may jeopardize the patient's safety if he or she continues in the study or if the investigator determines discontinuation is in the best interest of the patient.

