4.1 Rationale

Carfilzomib is marketed for multiple myeloma and this IST represents an off label use of carfilzomib; thus, the criteria for phase II designation have been met. This prospective, open-label, single-arm active treatment trial will establish the rate of response to carfilzomib (in addition to conventional therapy) for AMR after lung transplantation. This information will be necessary for use in planning further larger dual-arm placebo or active therapy controlled clinical trials. This trial will enroll 30 patients at the University of Pittsburgh Medical Center. The volume of lung transplants performed and the rate of diagnosis of AMR at UPMC will allow for adequate enrollment of study patients within the 3-year study period.

The dosing strategy of carfilzomib will follow that of the multiple myeloma schedule as described below in section 5.3. This dosing strategy has been well-studied in patients with myeloma (see trial designations below) and has proven to result in an acceptable AE profile for the patients with AMR after lung transplantation. In addition, our preliminary off label experiences with this dosing strategy have yielded an acceptable AE profile in lung transplant recipients with AMR.

Trial designations:

Carfilzomib has been evaluated in 2 completed Phase 1 studies (PX-171-001 and PX-171-002), 5 completed Phase 1b/2 studies (PX-171-003, PX-171-004, PX-171-005, PX-171-006, and PX-171-008), and in 1 completed, Phase 2, expanded-access study (Study 2011-002, Carfilzomib Multiple Myeloma Expanded Access Protocol [C-MAP]) that was co-sponsored by Amgen and the Multiple Myeloma Research Foundation.

Carfilzomib is currently being evaluated in 2 ongoing Phase 1 studies (CFZ001 [Renal] and CFZ002 [Hepatic]), 5 ongoing Phase 1b/2 studies (PX-171-007, PX-171-010, 2012-002 [CHAMPION 1], 2012-003 [CHAMPION 2], and CFZ004 [small cell lung cancer]), 4 ongoing Phase 3 studies (PX-171-009 [ASPIRE], PX-171-011 [FOCUS], 2011-003 [ENDEAVOR], and 2012-005 [CLARION]), and 2 ongoing Phase 1/2 studies sponsored by Ono Pharmaceutical Co, Ltd in Japan (ONO-7057-01 and ONO-7057-02).

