4.3.9 Hypogammaglobulinemia, total serum IgG < 700 mg/dL

4.4 Study Endpoints

4.4.1 Primary endpoint

The primary endpoint of this study is the absolute change in DSA strength, titer, and complement fixation from day 1 to day 42. DSA strength will be determined by Luminex single-antigen bead testing in the neat serum and quantitated in units of mean fluorescent intensity. DSA titer will be determined by Luminex single-antigen bead testing in the diluted serum to 1:16 and quantitated in units of mean fluorescent intensity. DSA complement fixation will be determined by C1q-based Luminex single-antigen bead testing in the neat serum and quantitated in units of mean fluorescent intensity.

A 1:1 retrospective control group including lung transplant recipients from the University of Pittsburgh with Antibody Mediated Rejection will be created to describe differences in the endpoints using the CFZ-based regimen vs. historic standard of care.

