5.1.1 Patient selection

Patients will be eligible for enrollment if they have met the diagnostic criteria for AMR as described in section 4.3.6. This involves the identification of DSA via Luminex SAB technology prior to day 1. Any patient who meets the diagnostic criteria after study initiation will be screened for enrollment. Patients who satisfy the inclusion and exclusion criteria will be approached to provide informed consent and enroll in the study.

A 1:1 retrospective control group including lung transplant recipients from the University of Pittsburgh with Antibody Mediated Rejection will be created to describe differences in the endpoints using the CFZ-based regimen vs. historic standard of care.

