5.13 Statistical methods

Data will only be analyzed in aggregate at study conclusion for the final enrolled patient on the efficacy and safety outcomes.

Descriptive statistics will be used to describe baseline and study characteristics of patients. Univariate parametric and nonparametric assessments, where appropriate, will be used to assess change from baseline in the efficacy and safety outcomes. Kaplan-Meier method will be used to describe freedom from endpoints and mortality in the patients treated with carfilzomib. Kaplan-Meier method will be used to visually represent the time to events and overall event rate in the patients in this pilot, not to compare events to any other group.

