5.13.3 Determination of sample size

The sample size for this trial is based on perceived appropriate enrollment of 10 patients per year for 3 consecutive years. Since this is a single-arm, active-treatment study, no such calculation of statistical power is needed to quantitate the sample size.

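### Section 5.9 selects replacement patients on expected completion, and Section 5.13 does not say whether replaced patients are analysed for efficacy or count towards the 30

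*Combined protocol and SAP*

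**What the plan says.** Three parts of the protocol bear on who is in the efficacy result.

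- **Enrolment.** Section 5.1.1: "Patients who satisfy the inclusion and exclusion criteria will be approached to provide informed consent and enroll in the study". The criteria in 5.1.2 and 5.1.3 cover the AMR diagnosis, prior testing, organ function, infection, pregnancy and medication. None concerns the likelihood of finishing a cycle.
- **Stopping and replacement.** Section 5.9 opens with "Patients will be removed from study continuation if the toxicities of therapy are deemed by the investigators to outweigh the potential benefit of therapy". Its next paragraph says that if patients stop the study drug early, "these patients may be replaced in the study by patients who are likely to complete at least 1 cycle of carfilzomib". It does not say who judges likely completion, or how.
- **Analysis.** Section 4.4.1: "The primary endpoint of this study is the absolute change in DSA strength, titer, and complement fixation from day 1 to day 42". The method in 5.13 is "Univariate parametric and nonparametric assessments, where appropriate, will be used to assess change from baseline in the efficacy and safety outcomes". Section 5.13.1 summarises discontinuations by patient. Neither 5.13 nor its subsections name an efficacy set, mention replacement, or give a rule for death or a missing day-42 value.

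On numbers, Section 4.1 says "This trial will enroll 30 patients at the University of Pittsburgh Medical Center" and that the trial is to yield a response rate for planning larger controlled trials. Section 5.13.3 bases the 30 on expected accrual and adds that "no such calculation of statistical power is needed to quantitate the sample size".

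**The concern.** In a single-arm trial the product is an estimate, so the main question is which patients it describes. The replacement rule affects that in two ways.

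1. **Selection.** A replacement must pass a judgement that the first patients did not face. If expected completion is related to response, the mix of treated patients shifts.
2. **Exclusion.** Replacement can be read as substitution, with the early stopper leaving the count of 30 and the replacement entering it. The toxicities named in 5.9 show that stopping need not be unrelated to outcome. With no efficacy set defined, whether early stoppers count could be settled after the results of an open-label trial are known.

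Either way, the day-42 DSA change and the response estimate might not describe everyone who was treated. The incidence outcomes in 4.4.3 have the same gap: 5.13.2 lists and summarises adverse events but defines no denominator.

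**Working it through.** **The plan's own figure.** Section 5.13.3 gives 10 patients per year for 3 years: 10 × 3 = 30. This reproduces the planned enrolment exactly and contains no allowance for replacement. No alpha, power, effect size or SD is stated, so replacement protects no stated precision or power target.

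**The texts side by side.**

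| Question | What the protocol gives |
|---|---|
| Is expected completion an eligibility criterion? | Not in 5.1.1 to 5.1.3; only in 5.9, for replacements |
| Are early stoppers still assessed? | Yes, in 5.4, as data collection |
| Are their efficacy data analysed? | Not stated in 5.13 |
| Do they count towards the 30? | Not stated in 4.1, 5.9 or 5.13.3 |

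**Illustration of size.** Every input below except 30 is an assumption. The documents give no early-stopping rate and no outcome for stoppers. Complete day-42 values are assumed.

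*Exclusion.* Suppose k patients are replaced and left out, 30 are counted, and 30 + k are treated. Let m be the mean MFI fall in the counted 30 and r × m the mean fall in the replaced patients.

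- All-treated mean = (30m + k·r·m) / (30 + k)
- Reported / all-treated = (30 + k) / (30 + k·r)

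| k | r = 0 | r = 0.5 | r = 1 | r = 1.5 |
|---|---|---|---|---|
| 3 | 33/30 = 1.10 | 33/31.5 = 1.05 | 1.00 | 33/34.5 = 0.96 |
| 6 | 36/30 = 1.20 | 36/33 = 1.09 | 1.00 | 36/39 = 0.92 |
| 9 | 39/30 = 1.30 | 39/34.5 = 1.13 | 1.00 | 39/43.5 = 0.90 |

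*Selection alone.* Suppose replaced patients are kept, and the k replacements have a mean fall s times that of the first 30 enrolled. The all-treated mean is then multiplied by (30 + k·s) / (30 + k).

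- k = 3, s = 0.5 and 1.5: 31.5/33 = 0.955 and 34.5/33 = 1.045, about −5% to +5%.
- k = 6: 33/36 = 0.917 and 39/36 = 1.083, about −8% to +8%.
- k = 9: 34.5/39 = 0.885 and 43.5/39 = 1.115, about −12% to +12%.

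*Response rate.* Take an assumed 18/30 = 60% in the counted patients and k = 3. The all-treated rate is 18/33 = 54.5% if none of the three replaced patients responded, and 21/33 = 63.6% if all did.

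Both routes can go either way. The exclusion effect is zero if replaced patients are retained or have the same mean outcome as the counted patients.

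**The case against.** The strongest reply is that the plan leans towards keeping early stoppers. Section 5.4 commits to all planned assessments after therapy stops, 5.13 speaks of analysis in aggregate, 5.13.1 summarises discontinuations by patient, and 4.1 counts patients enrolled. This stands in part. It makes an all-treated analysis feasible and rules out any claim that the plan excludes these patients. But collecting data is not a rule on who is analysed, and none of these sections says that a replaced patient's DSA or FEV1 change enters the result.

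A second reply is that the completion condition may do little. Section 5.9 does not waive 5.1, the exclusion for any uncontrolled comorbid condition already allows judgement, and one cycle is six doses over a minimum 16-day admission. That may be so. The effect may be small, but the condition remains undefined and applies only to replacements.

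A third is that the sizes rest wholly on assumptions. This is correct. No section supports any value of k, r or s, so the figures show scale, not evidence of bias.

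A reader might also infer that 5.4 and 5.7 contradict each other on follow-up. They need not: 5.4 concerns patients who stop therapy, and 5.7 concerns patients who leave the study.

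**Conclusion.** The point holds as an unstated analysis rule combined with a stated selection rule. Section 5.9 applies to replacements a condition that is absent from 5.1, and the plan does not say whether the patients they replace remain in the efficacy analysis or in the 30. It should be fixed before analysis.

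Two stronger readings are not supported. One is that the plan drops early stoppers and so inflates the DSA result: no section excludes them, and the direction is unknown. The other is that safety is untouched. All adverse events after consent are summarised and all deaths are recorded, but the incidence outcomes in 4.4.3 still lack a denominator.

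The size is not derivable from the documents. With 3 replaced patients left out and their mean fall assumed to be 0 to 1.5 times that of the counted 30, the reported fall is 1.10 to 0.96 times the all-treated fall. Larger k widens the range.

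**What to change.** 1. **Sections 5.9 and 4.1.** Delete the condition on expected completion. Replacements meet 5.1.2 and 5.1.3 only, and are added to the patients they replace rather than substituted for them. State in 4.1 whether 30 counts all treated patients.
2. **Section 5.13, analysis set.** Make all patients given at least one carfilzomib dose the primary efficacy set and the denominator for the 4.4.3 incidence outcomes. Report patients completing one cycle as a sensitivity analysis.
3. **Section 5.13, missing values.** Describe the day-42 mean change as an estimate among treated patients with day-1 and day-42 values, early stoppers included, and report how many values are missing and why. Add one all-treated sensitivity analysis that covers both kinds of gap: the median change with deaths ranked worst and other missing values set, for example, to no change from day 1. With 33 treated and 3 deaths, that median is the 17th largest fall, against the average of the 15th and 16th among the 30 survivors. For FEV1, limit this to patients with a day-1 value, because 5.1.2 lets intubated patients enrol without pulmonary function tests.
4. **Separate and minor.** Reconcile the commitment in 5.4 to complete all planned assessments after therapy stops with the statements in 5.4 and 5.6 that there are no research follow-up visits and that standard-of-care procedures are not done solely for research. State which follow-up applies to patients removed under 5.9.

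**Cost.** A short amendment and some analysis text. Items 1 to 3 need no new visits or tests. Item 1 adds no patients beyond those 5.9 already permits; at 10 per year, 3 replacements take 3/10 = 0.3 year with or without the change. The headline estimate may look less favourable.

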5.10 Study discontinuation

Amgen may discontinue the study prematurely for the following reasons: the incidence or severity of AEs in this study indicates a potential serious health hazard to patients, if enrollment is sufficiently poor, or if data recording is inaccurate or incomplete.

5.11 Post-trial access

No post-trial access of carfilzomib will be available to patients under the auspices of the study. Additional off label marketed carfilzomib may be given to patients outside of the study if necessary under the routine clinical care of the patient; however, such administration must not occur before day 90. If such administration occurs prior to day 90, this will reflect a protocol violation.

5.12 Assay methods

All blood draws will be acquired with usual clinical techniques. Luminex SAB and C1q-SAB and IgG subclass identification will be performed using usual clinical techniques as directed by the HLA lab under the CLIA approved standard practice. All routine labs (CBC, WBC differential, CMP) will be performed using usual clinical techniques as directed by the basic laboratory under the CLIA approved standard practice. PBMC isolation and subsequent exploratory testing will occur under usual investigatory techniques as directed by [name].

5.13 Statistical methods

Data will only be analyzed in aggregate at study conclusion for the final enrolled patient on the efficacy and safety outcomes.

Descriptive statistics will be used to describe baseline and study characteristics of patients. Univariate parametric and nonparametric assessments, where appropriate, will be used to assess change from baseline in the efficacy and safety outcomes. Kaplan-Meier method will be used to describe freedom from endpoints and mortality in the patients treated with carfilzomib. Kaplan-Meier method will be used to visually represent the time to events and overall event rate in the patients in this pilot, not to compare events to any other group.

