Conventional therapy for this problem, including plasma exchange and intravenous immunoglobulins, are limited and targeted at removal of circulating antibody; not at the antibody-producing apparatus, the plasma cell. Thus, our hypothesis is that the combination of conventional therapy with plasma-cell targeted therapy using the proteasome-inhibitor carfilzomib in symptomatic lung transplant recipients with AMR will improve/stabilize allograft function and result in depletion of the immunodominant DSA. In this proposal, we will conduct a pilot phase II open label observational trial in lung transplant recipients to test whether addition of carfilzomib to conventional therapy improves short-term outcomes after the diagnosis of antibody-mediated rejection, and to identify the cellular mechanisms that support these clinical benefits. Clinical and immune phenotyping of study subjects will advance our understanding of anticipated therapeutic responses. Specifically, cellular mechanistic studies to detect immune system changes that will enable us to phenotype LTRs with AMR and determine or predict risk and outcomes, such as BOS. Patients who have met the clinical diagnosis of AMR requiring therapy will be targeted for enrollment in the study and treated with the open-label carfilzomib-based combination protocol.

To execute this study, we have established the Combination Therapy with the Proteasome Inhibitor Carfilzomib for the Antibody-Mediated Rejection Diagnosis in Lung Transplantation (PICARD-Lung) Trial Study Group. This clinical trial will be executed at the University of Pittsburgh Medical Center leveraging the expertise and prowess of one of the highest-volume clinical lung transplant services worldwide, the [name] immunology lab, and the [name] immunohistochemistry and histocompatibility labs.

- 1: To test the hypothesis in a prospective interventional clinical trial that addition of carfilzomib to conventional therapy will result in depletion of the immunodominant DSA. In this trial, lung transplant recipients will be treated with the carfilzomib-based combination protocol and screened with Luminex single antigen bead testing to identify DSA burden by IgG and functional status by C1q before and after treatment.

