- 2: To test the hypothesis in a prospective interventional clinical trial that addition of carfilzomib to conventional therapy will result in improved or stabilized allograft function. In this trial, lung transplant recipients will be treated with the carfilzomib-based combination protocol and screened with pulmonary function testing to identify whether forced expiratory volume in 1 second returns to pre-AMR diagnosis level.
- 3: To test the hypothesis that lung transplant recipients with AMR have effector B cell/plasma cell populations that can be identified and characterized, and that carfilzomib alters these immune mechanisms. In this trial, we will determine the immunologic phenotype

of these patients and describe functional immune system changes in memory and effector cells, plasma cells, and respective pathologic and immunohistochemical correlates relevant to AMR.

The PICARD-Lung investigators and the study center are highly experienced clinical and translational investigations in lung transplantation. Successful completion of these specific aims will establish the safety and efficacy of combination therapy with carfilzomib/PLEx/IVIG for AMR after lung transplantation and elucidate important clinical and immunologic phenotypes and mechanisms associated with these outcomes. Thus, the results of this trial will advance treatment efforts for AMR, which are desperately needed, as well as provide important insights into the link between AMR and BOS, the latter of which significantly limits long-term outcomes in lung transplant recipients. Lastly, we fully anticipate this study will lay the foundation for future clinical and basic investigation, perhaps at the multi-center level, to further delineate the role and immune effects of carfilzomib in the treatment of AMR and the prevention of BOS.

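### Objectives 1 and 2 are worded as tests of adding carfilzomib, but the analysis is within-arm change on the combined regimen, and the control that could inform the added effect is not defined well enough to analyse

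*Combined protocol and SAP*

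**What the plan says.** **The aims.** Section 3.1 says the trial is meant "to test whether addition of carfilzomib to conventional therapy improves short-term outcomes after the diagnosis of antibody-mediated rejection". Objective 1 is the hypothesis that "addition of carfilzomib to conventional therapy will result in depletion of the immunodominant DSA", and objective 2 that "addition of carfilzomib to conventional therapy will result in improved or stabilized allograft function". The same section also describes both aims as before-and-after: DSA burden and "functional status by C1q before and after treatment", and lung function tests "to identify whether forced expiratory volume in 1 second returns to pre-AMR diagnosis level". It ends with "Successful completion of these specific aims will establish the safety and efficacy of combination therapy with carfilzomib/PLEx/IVIG". Section 4.1 gives a narrower purpose: the trial "will establish the rate of response to carfilzomib (in addition to conventional therapy"), as a basis for planning later controlled trials.

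**The treatment.** Sections 4 and 5.3 give every patient eight PLEX sessions and IVIG with carfilzomib. Section 5.3 says PLEX is there partly to take DSA out of the circulation, and IVIG partly to limit antibody rebound. Appendix A adds intravenous Medrol when cellular rejection (ACR) is also present.

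**The analysis.** Section 5.13 specifies "Univariate parametric and nonparametric assessments, where appropriate, will be used to assess change from baseline in the efficacy and safety outcomes". Kaplan-Meier curves are limited to the treated patients, and comparison with another group is ruled out.

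**The control.** The synopsis and sections 4.4.1, 4.4.2, 4.4.3 and 5.1.1 promise a 1:1 retrospective group of University of Pittsburgh lung recipients with antibody-mediated rejection (AMR), to describe endpoint differences against historic standard of care. Sections 5.13 to 5.13.3 do not mention it. The by-group statement in 5.13.1 covers only baseline and drug-administration summaries.

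**The concern.** The objectives name the effect of one component, while the analysis measures change on all components together. The primary endpoint is change in DSA from day 1 to day 42, and DSA is what PLEX is given to remove. A favourable change would therefore be expected to some degree, or at least be possible, without any contribution from carfilzomib. A report that follows 3.1 and 5.13 as written would credit that change to carfilzomib.

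The retrospective control is the only planned route to the added effect. Which historic cases are used, what their day 1 is and how the difference is summarised can all be settled after the treated results are known. Three further features bear on the comparison:

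- **Outcomes without a control counterpart.** The control sentence sits under safety outcomes that patients not given carfilzomib cannot have: organ failure attributed to carfilzomib (4.4.3.1), adverse events requiring dose modification (4.4.3.2) and death attributed to carfilzomib (4.4.3.7).
- **One-sided replacement.** Section 5.9 lets early discontinuers be replaced by patients likely to complete a cycle. Nothing equivalent applies to controls.
- **Deaths.** Death is among the endpoints to be described against the control, yet 5.13 keeps Kaplan-Meier to the treated group. No other method for comparing deaths is given.

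**Working it through.** **1. The plan's own figure.** Section 5.13.3 bases the sample size on 10 patients a year for 3 years: 10 × 3 = 30, which reproduces. No alpha, effect size, SD or success rule is given, so the figures below rest on assumptions: 30 analysed patients, two-sided 0.05, t-tests, and shifts in units of the SD of change. They show scale and do not predict the result. Section 5.13 also allows nonparametric methods.

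**2. Within-arm test with zero carfilzomib effect.** Let background therapy alone shift the endpoint favourably by δ SD. The paired t statistic has 29 degrees of freedom, noncentrality δ√30 and critical value 2.045. The probability of a significant favourable change is P(T > 2.045).

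| δ | δ√30 | Probability |
|---|---|---|
| 0 | 0 | 0.025 |
| 0.2 | 1.095 | 0.18 |
| 0.3 | 1.643 | 0.36 |
| 0.5 | 2.739 | 0.75 |

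**3. A 30 v 30 contrast.** A background shift equal in both groups cancels, so the probability returns to 0.025. That follows by construction and is not evidence that historic controls behave this way. Suppose instead that a confounding difference of c SD remains between the groups. The noncentrality is c/√(1/30 + 1/30) = c√15, with 58 degrees of freedom and critical value 2.002.

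| c | c√15 | Probability falsely favourable |
|---|---|---|
| 0.2 | 0.775 | 0.12 |
| 0.3 | 1.162 | 0.21 |
| 0.5 | 1.936 | 0.48 |

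The contrast removes only what the two groups share.

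**4. Precision of the contrast.** The unadjusted 95% half-width for a mean difference is t × √(1/a + 1/b). At 30 v 30 it is 2.002 × √(2/30) = 0.52 SD. If only 15 controls have usable records it is about 0.64 SD.

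**5. Direction of the background shift.** This is not known. PLEX lowers DSA, but 5.3 anticipates rebound. Appendix A puts the last PLEX of a cycle on day 15, and 5.6 allows ±14 days around day 42. For a patient given one cycle, the sample falls 28 − 15 = 13 to 56 − 15 = 41 days after the last PLEX. Section 5.3.1.1 allows a second cycle, so this gap does not hold for everyone. The documents give no day-42 change on PLEX/IVIG alone.

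**The case against.** This is a pilot, and a single-arm design with before-and-after measurement is legitimate. Section 3.1 itself frames the measurements that way, 4.1 says the purpose is to plan later controlled trials, and the control is meant only to describe differences. All of that stands: the design is not the error, and a response estimate for the combined regimen is useful. It does not rescue the wording about the added effect. A descriptive comparison also still needs a stated population, index day and summary.

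Three stronger readings are tempting and are not supported:

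- **A reader might infer that the results could neither support nor count against the objectives.** The objectives say the addition will result in depletion and in improved or stabilised function. If DSA does not fall, or FEV1 keeps declining, that counts against them as worded. The problem runs one way: a favourable change cannot be assigned to carfilzomib.
- **A reader might infer that the control has no selection rule at all.** Section 5.1.1 gives the centre, the diagnosis (defined in 4.3.6) and the ratio. What is missing is the period, the eligibility and the order in which cases are taken.
- **A reader might infer that adding the control comparison would give a valid test of carfilzomib.** Step 3 shows otherwise. Modest confounding makes the contrast falsely favourable well above the nominal rate, and historic controls come with no assurance against it.

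**Conclusion.** The point holds in limited form and should be fixed. The within-arm analysis in 5.13 describes carfilzomib plus PLEX/IVIG, while objectives 1 and 2 are worded as tests of the addition. The only comparison that could inform the added effect lacks a period, eligibility, sampling order, index day and estimator, and it is absent from the statistical section.

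Under the stated assumptions, a favourable background shift of 0.2 to 0.5 SD alone yields a significant favourable within-arm change with probability 0.18 to 0.75. A defined 30 v 30 contrast is better directed at the question but remains a confounded and imprecise estimate. The true background shift is not in the documents, and neither its size nor its direction should be presumed. Second cycles, which controls cannot have, add to the uncertainty at days 42 and 90.

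**What to change.** 1. **Interpretation.** In 3.1 and 5.13, state that the within-arm change describes response to carfilzomib plus PLEX/IVIG and does not isolate carfilzomib.
2. **Controls.** In 5.13, define them as consecutive AMR cases that meet 4.3.6 and the applicable 5.1.3 exclusions and were treated with PLEX/IVIG without a proteasome inhibitor. Take them from a stated calendar period counted back from a fixed anchor date. Set day 1 as the first PLEX and use the same day-42 window. Report use of the 5.3.3 drugs by group.
3. **Treated set.** Include every patient given any carfilzomib, including those replaced under 5.9. Report how many began a second cycle before day 42 or day 90. Keep them in the main analysis and add a sensitivity analysis without them.
4. **Estimator.** Report the day-42 regimen-versus-control difference with a 95% CI, adjusted for the day-1 value and rank-based for MFI, as descriptive estimation. By group, give assay and FEV1 availability, deaths before day 42, ACR grade and Medrol use. State the residual confounding.
5. **Outcomes.** Remove 4.4.3.1, 4.4.3.2 and 4.4.3.7 from the control comparison. Compare deaths as proportions, since 5.13 limits Kaplan-Meier to the treated group. Present any-AE rates without a formal contrast, because trial events are elicited by questioning (6.2.2) and control events come from charts.

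**Cost.** Wording, one control-definition paragraph, and chart abstraction for a group already planned. Section 5.4.1 lists the Luminex assays and lung function tests as standard of care, but the documents do not show that historic cases have 1:16 or C1q results near day 42. The claim becomes less favourable and precision is low (half-width about 0.52 SD at 30 v 30). No change to trial patients' treatment or visits is needed.
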